Participants were sampled at random from a population listing from AHRI/Africa Centre's surveillance. AHRI's surveillance is organized by geographically defined week blocks. Specific week blocks were chosen for this study based on the timing of AHRI's surveillance. We included respondents residing in week blocks where AHRI was scheduled to conduct its annual surveillance and HIV testing offer about 6-8 weeks after the baseline survey.

Details on the Sampling Strategy are contained in Appendix A.

We chose a target sample size of 450 individuals. The final actual sample size will be determined based on the number of successful interviews achieved within a pre-specified period, from a pre-specified roster of eligible participants. The number of eligible participants included in the study roster is based our target of 450 baseline interviews conducted. Based on prior studies of this age group at AHRI, we anticipate that we will be able to find and recruit 50- 60% of the eligible population. We anticipate that our study team is capable of conducting 60-75 interviews per week. We therefore sampled 120 individuals in each of seven week-blocks for a total of 840 individuals eligible for recruitment. The final sample size was the number of respondents successfully interviewed from the pre-specified study rosters.

With a target sample of 450 individuals, this study is powered at 80% to detect a 0.26 standard deviation difference in outcomes between the treatment and pooled control groups.

Example 1) We are powered to detect an increase in subjective (perceived) life expectancy from 50 to 54 years, assuming a standard deviation of 15 years. The baseline numbers – 50, $sd=15$ – are based on survey pre-tests conducted as part of a prior study: "Life plans of young adults in rural KZN: a qualitative study". A four-year increase would be about a quarter of the actual change in life expectancy that occurred between 2003 and 2014.

Example 2) We are powered to detect an increase in the proportion using the HIV testing voucher (or taking up the job search skills workshop) from 10% to 20%. As this is a pilot study, we are only powered to detect intervention effects if they are large.

A8. Interventions and Randomization

A8.1. Study Arms

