The study is a population-based randomized controlled trial. To reduce potential for contamination, treatment assignment will be determined at the level of the household, such that if there are multiple eligible participants per household, they will receive the same treatment. Households will be randomized to study arm *ex ante*, i.e. before going into the field. *Ex ante* randomization has two benefits. First, as a quality control, *ex ante* randomization limits the opportunity for violations of treatment assignment. Second, because the study is nested in the AHRI population surveillance, *ex ante* randomization enables us to achieve balance across study arms with respect to several baseline characteristics of interest among eligible participants. We will use a constrained randomization approach to achieve approximate balance on: sex, age, whether the person was in school, orphans status, HIV positive status, HIV negative status (unknown is the third category), and household asset quintile. These factors were selected because of their potential influence on survival expectations. (For further details on randomization procedures, please see Appendix C.)

We note that sampling and randomization will be conducted using AHRI's public use (de-identified) data. We will provide a list of public use identifiers and treatment assignments to AHRI's data management staff, and they will create an operational database to be used during data collection. Information on the characteristics above (e.g. HIV status) will never be linked with personally-identifiable information.

Participants will be randomized using a ratio of 50% active treatment, 25% attention placebo control, 25% pure control.

	Active Treatment Video	Attention Placebo Video
Arm 1, Active Treatment	X	
Arm 2, Attention Placebo Control		X
Arm 3, Pure Control		

A8.3. Blinding

Participants and interviewers

During recruitment, consent, and the first half of the baseline survey, participants and interviewers will be blinded as to the participant's treatment assignment. Randomized treatment assignment will be revealed at the moment when participants received the intervention. However, we will not indicate to the participants whether the video they see is the treatment or attention placebo video.

Researchers

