The researchers will be blinded to the randomization status of participants throughout the data collection, extraction, and cleaning/quality control process, up until the date when randomized assignments are unmasked. To maintain blinding of treatment assignments vis-à-vis the research team during the study, we will use the following procedures:

- Treatment assignment will be stored as a hidden field in the REDCap database. I.e. during the baseline survey it will generate a pop-up message telling the interviewer to show the participant the active treatment video, active control video, or no video, however this field will not be visible to anyone on the research team.
- The treatment assignment field will not be exported during routine quality control procedures.
- Treatment assignment will be extracted along with study ID into its own table and will not be merged with any of the other data until randomization is unblinded.
- Randomization will be unblinded only after the final Pre-Analysis Plan is posted to www.clinicaltrials.gov. In developing our pre-analysis plan, we conducted some descriptive analysis of the blinded baseline pre-intervention survey data. Additionally, we monitored overall levels of uptake of the HIV testing voucher and job search training workshop in order to determine potential statistical power with these outcomes. For guidance on using baseline data to inform Pre-Analysis Plans, see Olken (2015).
- We will submit an update to our clinicaltrials.gov study profile after treatment assignment is unblinded, noting the date when we have done so.

As this is a short (4-month) pilot study and the intervention is minimal risk, we do not have a DSMB and do not have stopping rules for the trial based on preliminary analysis of efficacy.

A9. Baseline interview and intervention

The baseline survey visit is designed to take about 1.5 hours, and consists of the following sub-components:

A9.0. Recruitment and Informed Consent

Potential respondents will be recruited via visits to their homesteads. Permission will be obtained from the head of household to enter and to speak to the sampled participant. The study will be described and participants will provide written informed consent to participate in the study, including the baseline visit, a follow-up visit, and permission to link with demographic surveillance data. See Appendix B for the approved consent form.

A9.1. Survey module

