
Savings choice. Lastly, all participants will be provided with a labeled savings tin. During the disbursement of participant compensation (R100), the participants will be given the opportunity to save a portion of the money by placing it in the sealed savings tin. We will record the amount of money the participant chooses to save and hold a brief discussion with the participant about saving for the financial aspects of their future goals. We provide this option for study participants so that we can immediately measure intentions for future-oriented behavior and to estimate the

video's short-term effect based on differences in the amount saved between the treatment and control groups.

A10. Follow-up interview at 2 months

Study participants will be contacted 2 months after their initial interview and provided with a follow-up survey that measures survival expectations, locus of control, life satisfaction, mental health, savings, health behaviors, time use, and HIV-related attitudes and beliefs. Participants will receive R50 in compensation for participation in the follow-up survey.

A11. Follow-up in the AHRI Surveillance

Home-based HIV testing. Data from this study will be linked at the individual level to the AHRI/Africa Centre population surveillance. The baseline survey is timed so that, about 6-8 weeks afterwards, the same household will be visited by the AHRI surveillance team for their routine annual surveillance visit. During this visit, all people ages 15 and older are offered home-based HIV testing and counseling, with referral to the public sector HIV program. Uptake of HIV testing in the AHRI surveillance visit at 6-8 weeks will be combined with use of the HIV testing voucher offered at baseline, to assess impacts on HIV testing uptake. Linkage with the surveillance will be conducted by AHRI data management staff.

Other outcomes. Participants will be followed up in future rounds of AHRI's routine population surveillance. In addition to HIV testing, the AHRI surveillance collects information on schooling, employment, and migration, among other outcomes, and is also linked to the public sector clinical record system. These linkages will be conducted by AHRI data management after data are de-identified.

A12. Project Timeline

April 2016 – December 2016	formative qualitative research
December 2016 – April 2017	creation of video intervention
May – July 2017	REDCap database development, pre-testing

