June 2017	Registered on www.clinicaltrials.gov
August 2017	Recruitment and training of field interviewers
September – October 2017	Baseline survey and intervention
September – November 2017	Job search workshops, HIV testing vouchers
November – December 2017	Follow-up survey, home-based HIV testing

December 2017	Updated on www.clinicaltrials.gov
January – August 2018	Data extraction, quality checks, passive follow-up of HIV testing in the AHRI surveillance
September 17, 2018	Final Protocol and Pre-Analysis Plan posted to www.clinicaltrials.gov
September 18, 2018	Randomization status unblinded to researchers and posted to www.clinicaltrials.gov
March 2018 – January 2019	Analysis and preparation of manuscripts

A13. Funding and Registration

This randomized trial was jointly funded by two grants from the National Institutes of Health: 1K01MH105320 ([name]) “Economic, health, and behavioral dimensions of HIV treatment scale-up” and 1R01HD084233 ([name]/[name]) “Causal pathways to population health impact of HIV antiretroviral treatment”.

The trial is registered on www.clinicaltrials.gov as NCT03215901.

* * *

B. PRE-ANALYSIS PLAN

B1. Outcomes Variables and Definitions

B1.1 Primary Outcome Measures

Behaviors

1. Participation in HIV testing

Definition: Use of HIV testing voucher to be provided OR participation in HIV testing during surveillance household survey visit conducted at 1 to 2 months follow-up.

[Time Frame: 2 months]

2. Composite measure of future-oriented behaviors

Definition: Count variable (range 0:3) equal to the sum of the following indicators:

- Participation in HIV testing (either via the voucher or home-based testing)
- Attendance at a job search skills workshop: 1=attended
- Allocation of funds to savings tin during baseline interview: 1=participant allocated at least 50 Rand (out of 100 Rand) to the savings tin

Beliefs and Attitudes

3. Change in subjective life expectancy (at 2 months)

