Our primary analyses will assess: *intervention video (arm 1, 50%) versus no intervention video (arms 2 and 3, 50%)*. This is the highest powered test we have. It is justified under the *a priori* assumption that the attention placebo control video has no effect on outcomes. Indeed, this is the same assumption that is made (implicitly) any time a placebo control is used, with the assumption justified by the design of the placebo as not having any theoretically active components. We note that this primary analysis rests on an *a priori* assumption. We are not powered to test the null hypothesis that Arms 2 and 3 are the same. And because of limited power, failure to reject the null hypothesis that arms 2 and 3 are the same would not be strong evidence that the null hypothesis is true. Hence, approach 1 is identified under an *a priori* assumption of no difference between arms 2 and 3.

In secondary analyses, we will loosen the a priori assumption and now compare:
A. intervention video (arm 1, 50%) versus attention placebo control (arm 2, 25%)
This comparison assesses the impact of information on survival gains due to ART on outcomes, holding constant the nature of the video intervention (attention control). Therefore, it comes closest to capturing the theoretical construct of interest.

B. intervention video (arm 1, 50%) versus pure control no video (arm 3, 25%)
This comparison assesses the impact of the informational video vis-à-vis standard of care, which is no video. This comes closest to capturing the effect of policy interest. Additionally, this comparison insures us against the possibility that our a priori assumption is incorrect (i.e the placebo video does affect outcomes), giving us an estimate of effect that does not include the effect of the placebo.

B3. Assessment of Balance

We conducted constrained randomization to ensure balance among individuals who were sampled and eligible to participate in the study. However, balance on these factors – as well as other factors not considered in the randomization – is unknown among the participants who are actually recruited into the study.

We will assess balance on the following characteristics that were included in the randomization: sex, age, whether the person was in school, orphan status, HIV positive status, HIV negative status (unknown is the third category), and household asset quintile.

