We will additionally assess balance on all primary and secondary outcomes described above that are measured at baseline.

Through linkage to the AHRI surveillance, we will additionally assess balance on: whether the person has a child; household size; distance to the nearest clinic, whether anyone in the household died from HIV in the prior 10 years; whether anyone in the household is receiving public sector ART at time of baseline.

For each baseline covariate, we will report a t-test for the null hypothesis of equal means in Arm 1 vs. Arms 2+3 (pooled).

B4. Statistical analysis of treatment effects

All statistical analyses will involve comparisons across the treatment arms described above. For each outcome, we will generate the following data:

Example Results Table (fake data)

	Sample Means				Treatment Effect Estimate (95% CI)		
	Arm 1, n=XXX	Arms 2+3, n=XXX	Arm 2, n=xxx	Arm 3, n=xxx	Crude difference	Adjusted for design variables ^a	Adjusted for design, strong predictors, and baseline imbalance ^b
Outcome 1	1.2	1.5			-0.3 (-0.5 to 0.2)	-0.3 (-0.5 to 0.2)	-0.3 (-0.5 to 0.2)
			1.7		-0.5 (-0.8 to 0.0)*	-0.5 (-0.7 to 0.0)*	-0.5 (-0.7 to 0.0)*
				1.4	-0.3 (-0.5 to 0.3)	-0.3 (-0.5 to 0.2)	-0.3 (-0.5 to 0.2)
Outcome 2							
...							
Outcome k							

^aDesign variables are those variables on which balance was explicitly assessed during randomization. ^bStrong predictors of the outcome are those factors in the baseline balance table that are adjusted differences include regression adjustment for stratifying variables, variables used in the constrained randomization, and variables that were not balanced at baseline despite randomization (p-value <0.1 in F-test).

Sample means will be reported for Arm 1, the combined control (Arms 2+3), and for Arm 2 and 3 separately. When assessing changes from baseline to follow-up, we will simply define the outcomes as within-subject “differences” to facilitate comparisons with other outcomes observed only after the intervention.

Crude comparisons of outcomes between treated and comparison arms will be assessed in linear regression models, regressing the outcome on an indicator for treatment arm and indicators for week-block, a stratification variable. We will adjust our standard errors for clustering at the household level, given that error terms without households may be correlated.

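### Composite primary outcome 2 includes a savings choice made in session after the interviewer is unblinded; add a pre-specified 0:2 version (HIV testing plus workshop attendance) as a sensitivity analysis.

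*Combined protocol and SAP*

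**What the plan says.** **Blinding.** A8.3 keeps participants and interviewers blinded through recruitment, consent and the first half of the baseline survey. After that, "Randomized treatment assignment will be revealed at the moment when participants received the intervention". The mechanism is a pop-up "telling the interviewer to show the participant the active treatment video, active control video, or no video". A8.3 adds that participants are not told whether the video they see is the treatment or the attention placebo.

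**Order of the visit.** Under A9.3 and A9.4 the visit continues with the re-survey, the HIV testing voucher, the condom offer and the workshop reservation. The savings choice from the R100 compensation comes last. For that step the protocol says: "We will record the amount of money the participant chooses to save and hold a brief discussion with the participant about saving". A9.4 describes this as an immediate measure of intentions. It gives no script for the discussion and does not say whether the discussion comes before or after the choice is recorded.

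**Endpoint.** B1.1 defines primary outcome 2 as a count from 0 to 3. One item is "Allocation of funds to savings tin during baseline interview", scored 1 for at least R50 out of R100. The other two are HIV testing (voucher or surveillance visit) and workshop attendance. A4 gives the same three items. A5 lists voucher use and surveillance testing separately; the count of three used here follows A4 and B1.1.

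**Related analyses.** HIV testing is also primary outcome 1. Workshop attendance, the amount saved at baseline and savings at 2 months are secondary outcomes. B6 lists three robustness checks: a logistic model, a restriction by known HIV status, and removal of inconsistent answers. None removes the savings item. B7 makes no multiplicity adjustment for primary outcomes.

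**The concern.** The three items differ in how they are observed. Voucher use comes from the pharmacies, home testing from the surveillance team, and attendance from the workshop roster, all after the visit. The savings item is fixed face to face, with study staff present, after the interviewer has learned the arm. In Arm 1 it also follows a video that, by the account in A8.1, shows people motivated to invest in themselves, their families and a small business.

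A warmer savings discussion in Arm 1, or a participant's wish to act in line with the video just seen, could raise that item alone. Equal weighting passes the shift straight into the composite. Because the composite is tested at the full 5% level, a significant result could be reported as a general effect on future-oriented behavior when only the in-session item had moved.

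**Working it through.** **1. The plan's own figure.** A7 states: "With a target sample of 450 individuals, this study is powered at 80% to detect a 0.26 standard deviation difference in outcomes". Allocation under A8.2 is "Participants will be randomized using a ratio of 50% active treatment, 25% attention placebo control, 25% pure control", and the primary contrast in B2 is Arm 1 against Arms 2 and 3 pooled, so 225 against 225. The power statement gives no alpha; two-sided 0.05 is assumed from the 95% CIs in B4. Power = Φ(0.26 × √(225/2) − 1.96) = Φ(0.798) = 78.7%. The exact 80% detectable effect is (1.96 + 0.8416) × √(2/225) = 0.264 SD. The plan's figure reproduces after rounding.

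**2. Assumptions for the composite.** The documents give no observed rates and no expected rate for saving at least R50 or for the combined testing outcome. Assumed control rates are testing 30-50%, workshop 10-20% and saving 20-70%. The items are taken as independent and household clustering is ignored. The savings rate in Arm 1 is raised by b; testing and attendance are unchanged.

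**3. Formulas.** Variance of the count in one group: V = Σ p(1 − p). SE of the difference = √((V0 + V1)/225). Standardized shift d = b/√((V0 + V1)/2). Probability of significance = Φ(z − 1.96) + Φ(−z − 1.96), with z = b/SE.

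**4. Worked example.** Testing 40%, workshop 10%, saving 50%: V0 = 0.24 + 0.09 + 0.25 = 0.58.
- b = 0.10: V1 = 0.24 + 0.09 + 0.24 = 0.57; SE = √(1.15/225) = 0.0715; z = 1.40; d = 0.132; 28.8% significant.
- b = 0.20: V1 = 0.24 + 0.09 + 0.21 = 0.54; SE = √(1.12/225) = 0.0706; z = 2.83; d = 0.267; 80.9% significant. This d is about the plan's 0.26 SD.

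**5. Range over the assumed rates.**

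| Savings-only shift | Composite significant (nominal 5%) |
|---|---|
| 5 points | 10-12% |
| 10 points | 26-33% |
| 20 points | 75-89% |

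For 10 points, the low end is testing 50%, workshop 20%, saving 45%: V0 = V1 = 0.6575, z = 1.31, 25.8%. The high end is testing 30%, workshop 10%, saving 70%: V0 = 0.51, V1 = 0.46, z = 1.52, 33.1%.

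**6. Checks.** Simulation of 10,000 trials at testing 30%, workshop 10%, saving 50% gave a significant result in favor of the video in 10.8%, 30.6% and 83.4% for shifts of 5, 10 and 20 points; the formula gives 10.7%, 30.0% and 83.0%. Positive correlation between items widens the composite SD and weakens the effect: at testing 50%, workshop 20%, saving 50%, a pairwise correlation of 0.2 lowers the 10-point figure from 25.8% to 19.8% and the 20-point figure from 75.5% to 61.2% (favorable direction only).

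**7. What the plan already reveals.** B4 fits the same linear model to every outcome. With the same covariates and participants, the coefficient for a sum equals the sum of the coefficients. The reported effects on testing and attendance therefore add up to the 0:2 effect, and subtracting that from the composite effect gives the effect on the savings indicator. The 0:2 confidence interval cannot be obtained this way, because it needs the covariance of the two estimates.

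**The case against.** The strongest reply is that the plan already disaggregates. A4 and B1 set out separate tests for HIV testing, workshop attendance and savings, and by the additivity in step 7 a savings-only pattern would be visible to anyone who compares the rows. This stands. A reader might infer that the plan has no means of telling a savings artefact from a change in the other behaviors; the documents do not support that. What is missing is a joint estimate with its own interval and a stated rule for describing a composite driven by savings.

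Second, some masking remains. Participants are not told which video is the treatment, the placebo video is matched on length, pace, tone and narrative structure (A8.1), and B2 compares Arm 1 with Arm 2. This goes some way against a wish to please. It does not blind the interviewer, and half of the pooled control group sees no video.

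Third, the plan does not claim that the composite measures only later behavior. A9.4 says openly that the savings choice measures immediate intentions, and persistence has its own secondary outcome, with the tin opened at 2 months. This also stands. The point concerns how a positive composite is described, not whether savings belongs in it.

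Fourth, a 10-point shift equals the 10% to 20% change that A7 uses as an example of a large effect. A small interviewer effect would usually not make the composite significant by itself.

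**Conclusion.** The point holds as a cheap improvement. One of three equal items in primary outcome 2 is fixed in session after the interviewer knows the arm, and no planned check re-estimates the composite without it. Under the stated assumptions, a shift in that item alone raises the chance of a significant composite from 5% to about 10-12% (5 points), 26-33% (10 points) or 75-89% (20 points). These are hypothetical shifts on assumed rates; clustering and positive correlation between items would reduce them.

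Three stronger readings go beyond the documents. Nothing shows that bias occurred. No section states that the person who shows the video also runs the savings step; a single visit and interviewer-specific respondent lists (Appendix A) make it likely. Nor is the interval between video and savings choice given: the choice comes last in a visit of about 1.5 hours, after the re-survey and three other offers.

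**What to change.** In B6, add one check on primary outcome 2: recompute it as a 0:2 count (HIV testing plus workshop attendance), using the same model, the same Arm 1 against Arms 2+3 contrast and the same household-clustered standard errors. Report the estimate and 95% CI beside the 0:3 composite and the effect on the at-least-R50 indicator.

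In B1.1 or B6, state that if the 0:3 result rests mainly on the savings item, it will be described as an in-session savings effect observed by an unblinded interviewer. The meaning of mainly should be fixed in advance; one option is more than half of the 0:3 estimate, which additivity makes directly computable.

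The cost is a few lines of text and two regressions on data already collected. A12 places unblinding the day after the plan is posted, so the addition counts as pre-specified only if made before then.

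The 0:2 count is narrower and drops any genuine savings effect. In the worked example its 95% CI would be about ±1.96 × √(2 × 0.33/225) = ±0.11 on the count scale. It is also not free of interviewer influence, because the voucher information and the workshop reservation fall in the same visit. It should therefore sit beside the composite as a sensitivity analysis and not replace it.
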